### **2.3.1.1. Other Clinically Relevant Information**

Additional details concerning safety observations from clinical studies and for which a causal association has not been established or which are of minimal clinical significance may be found in the Investigator's Brochures .

#### ***Adverse Events of Special Interest:***

##### Seizure

Several cases of seizure have occurred during the cabotegravir program. These cases have had alternative explanations for their occurrence. Overall, there is not convincing evidence that cabotegravir exposure may be causally associated with seizure or with reduction of seizure threshold, due to the low frequency of reports, the confounders present in the cases received to date and lack of any pre-clinical signal or identified plausible mechanism. However, seizure and seizure-like events are considered as AEs of special interest for CAB. Subjects with an unstable or poorly controlled seizure disorder will be excluded from study participation. All cases of prior seizure history should be discussed with the Medical Monitor prior to enrolment. Report any cases of seizure or seizure like events immediately.

### **2.3.2. Benefit Assessment**

The antiviral activity against HIV-1 of CAB has been well established through Phase 2 and Phase 3 studies. RPV is an established antiviral agent against HIV-1 in treatment naive patients, with long term durability (>96 weeks in Phase 3 and >240 weeks in Phase IIb).

Participants receiving CAB LA + RPV LA are anticipated to benefit from maintenance of virological suppression using LA agents. Participants randomized to receive CAB LA+ RPV LA Q4W or Q8W weekly dosing will not need to take concomitant daily oral therapy. Adherence in these participants is expected to be improved and will be directly observed during IM injections. Efficacy of this two-drug regimen, as IM agents, has been demonstrated through Week 96 of the ongoing 200056, 201584 and 201585 studies. The reduction in ART, and the discontinuation of NRTIs, may offer long term safety and tolerability benefits in these participants.

### **2.3.3. Overall Benefit:Risk Conclusion**

Taking into account the measures taken to minimize risk to participants participating in this study, the potential risks identified in association with CAB LA and RPV LA Q4W and Q8W regimens, and the study as a whole are justified by the anticipated benefits that may be afforded to treatment-experienced patients with HIV-1 infection.

### 3. OBJECTIVES AND ENDPOINTS

Objectives	Endpoints
Primary	
To demonstrate the non-inferior antiviral activity of CAB LA + RPV LA every 8 weeks (every two months) compared to CAB LA + RPV LA every 4 weeks (monthly) over 48 weeks in suppressed HIV-1 infected antiretroviral therapy (ART)-experienced participants	Proportion of participants with plasma HIV-RNA greater than or equal to 50 copies/mL as per Food and Drug Administration (FDA) Snapshot algorithm at Week 48 (Intent-to-Treat Exposed [ITT-E] population)
Secondary	
To demonstrate the antiviral and immunologic activity of CAB LA + RPV LA every 8 weeks compared to CAB LA + RPV LA every 4 weeks	
Proportion of participants with plasma HIV-1 RNA <50 c/mL (c/mL) at Week 24, Week 48, Week 96, and Week 152 using the FDA Snapshot algorithm (Intent-to-Treat Exposed [ITT-E] population)
 
Proportion of participants with protocol-defined confirmed virologic failure (CVF) through Week 24, Week 48, Week 96, and Week 152
 
Proportion of participants with HIV-RNA greater than or equal to 50 c/mL as per FDA Snapshot algorithm at Week 24, Week 96, and Week 152
 
Absolute values and changes from Baseline in viral load and CD4+ cell counts over time including Week 48, Week 96, and Week 152

To evaluate the safety and tolerability of CAB LA + RPV LA every 8 weeks compared to CAB LA + RPV LA every 4 weeks	
Incidence and severity of AEs and laboratory abnormalities over time including Week 24, Week 48, Week 96, and Week 152
 
Proportion of participants who discontinue treatment due to AEs over time including Week 24, Week 48, Week 96, and Week 152
 
Change from Baseline in laboratory parameters over time including Week 48, Week 96, and Week 152

Objectives	Endpoints
To assess viral resistance in participants experiencing protocol-defined confirmed virologic failure	Incidence of treatment emergent genotypic and phenotypic resistance to CAB, RPV through Week 24, Week 48, Week 96, and Week 152
To characterize CAB and RPV concentrations and population pharmacokinetics and identify important determinants of variability	
Plasma PK parameters for CAB LA and RPV LA (when evaluable, <math>C_{trough}</math>, concentrations post dose [<math>\sim C_{max}</math>], and area under the curve [AUC])
 
Demographic parameters including, but not limited to, age, sex, race, body weight, body mass index, and relevant laboratory parameters will be evaluated as potential predictors of inter- and intra-participant variability for pharmacokinetic parameters

To assess preference for CAB LA + RPV LA every 8 weeks or CAB LA + RPV LA every 4 weeks LA compared to oral antiretroviral (ARV)
 
To assess preference for CAB LA+ RPV LA every 8 weeks compared to CAB LA + RPV LA every 4 weeks
	Preference for CAB LA + RPV LA every 8 weeks or CAB LA + RPV LA every 4 weeks compared to oral ARV and preference for CAB LA + RPV LA every 8 weeks compared to CAB LA + RPV LA every 4 weeks will be assessed using a preference questionnaire at week 48 (or Withdrawal).
To assess patient reported health-related quality of life, treatment satisfaction, injection tolerability, and treatment acceptance.	
Change from Baseline (Day 1) in HRQoL at Week 24, and Week 48 (or Withdrawal)
 
Change from baseline (Day 1) in total “treatment satisfaction” score, and individual item scores of the HIV Treatment Satisfaction Status Questionnaire (HIVTSQs) at Week 24, 48, and 152 (or Withdrawal)
 
Change in treatment satisfaction over time using the HIV Treatment Satisfaction Change Questionnaire HIVTSQc at Week 48 (or Withdrawal).
 
Change from Week 8 in Dimension scores (“Bother of ISRs”, “Leg movement”, “Sleep”, and “Injection Acceptance”) and individual item scores assessing pain during injection, anxiety before and after injection, willingness to be injected in the future and overall satisfaction with mode of

Objectives	Endpoints
	
administration over time will be assessed using the Perception of iNjection questionnaire (PIN) at Weeks 8, 24, 48 and 152 (or Withdrawal)
 
Change from Baseline (Day 1) in treatment acceptance at Weeks 24, 48 and 152 (or Withdrawal) will be assessed using the “General acceptance” dimension of the Chronic Treatment Acceptance (ACCEPT) questionnaire

Exploratory	

To evaluate the antiviral and immunologic effects, safety and tolerability, and viral resistance of CAB LA + RPV LA for all participants in the Extension Phase.
	
Proportion of participants with plasma HIV-1 RNA <50 c/mL over time
 
Proportion of participants with confirmed virologic failure over time
 
Incidence of treatment emergent genotypic and phenotypic resistance to CAB and RPV in over time
 
Incidence and severity of AEs and laboratory abnormalities over time
 
Proportion of participants who discontinue treatment due to AEs over time
 
Absolute values and changes in laboratory parameters over time
 
Incidence of disease progression (HIV-associated conditions, acquired immunodeficiency syndrome [AIDS] and death)

To explore the effect of patient characteristics on virologic and immunologic responses to CAB LA+ RPV LA every 8 weeks compared to CAB LA + RPV LA every 4 weeks
	
Proportion of participants by patient subgroup(s) (e.g., by age, gender, BMI, race, HIV-1 subtype, Baseline CD4+, type of oral treatment [NNRTI, PI, or INSTI], duration prior CAB LA and RPV LA exposure [0 weeks, 1-24 weeks, > 24 weeks]) with HIV-RNA greater than or equal to 50 c/mL over time including Week 48, Week 96, and Week 152 using the Snapshot algorithm for the

Objectives	Endpoints
	ITT-E population  Change from Baseline in CD4+ cell counts by subgroups at Week 48, Week 96, and Week 152
To explore relationship(s) between plasma concentrations of CAB and RPV and pharmacodynamic endpoints.	Relationship between plasma CAB and RPV concentrations and virologic, immunologic responses, and/or occurrence of adverse events [AEs] over time.
To assess reason for switching using a single question.  To assess reason for continuation using a single question	For patients randomized from oral SOC, the reasons for willingness to switch ART at baseline (Day 1) will be assessed  For patients randomized from CAB LA + RPV LA every 4 weeks in ATLAS, the reasons for willingness to continue long-acting ART at baseline (Day 1) will be assessed
To assess preference for CAB LA + RPV LA every 8 weeks or every 4 weeks compared to daily oral for participants receiving oral bridging during the Maintenance and/or Extension phases	Preference for CAB LA + RPV LA every 8 weeks or every 4 weeks compared to daily oral for participants receiving oral bridging during the Maintenance and/or Extension phases will be assessed using a preference questionnaire at Week 152 or Withdrawal

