### 1.1. Rationale

The 207966 (ATLAS-2M) study is being conducted to establish if human immunodeficiency virus type 1 (HIV-1) infected adult participants with current viral suppression (HIV-1 RNA <50 c/mL) remain suppressed upon administration of a two-drug intramuscular (IM) long-acting (LA) regimen of cabotegravir (CAB) and rilpivirine (RPV) administered every 8 weeks (Q8W; every 2 months). This study is designed to demonstrate the non-inferior antiviral activity of CAB LA 600 mg + RPV LA 900 mg administered every 8 weeks compared with CAB LA 400 mg + RPV LA 600 mg administered every 4 weeks (Q4W; monthly) over a 48-week treatment period. ATLAS-2M will also provide comparative data on antiviral activity, safety, tolerability, and patient satisfaction through Week 152.

Two groups of participants with demonstrated virologic suppression will be enrolled into ATLAS-2M including participants who at Screening are 1) receiving oral standard of care triple antiretroviral therapy (SOC) or 2) receiving a two drug IM regimen of Q4W CAB LA + RPV LA. The majority of participants in ATLAS-2M will rollover from the ongoing 201585 (ATLAS) trial and additional participants on SOC will also be included in order to support a targeted total sample size of approximately 1020 participants. Participants entering on SOC treatment consisting of a stable antiretroviral (ARV) regimen containing 2 nucleoside reverse transcriptase inhibitors (NRTIs) plus an integrase inhibitor (INI), non-nucleoside reverse transcriptase inhibitor (NNRTI), or a protease inhibitor (PI), will therefore either enter as new study participants or will rollover from the ongoing ATLAS trial. All participants entering on Q4W CAB LA + RPV LA will be rolled over from the ATLAS trial.

ATLAS is a Phase III, randomized, multicenter, parallel-group, non-inferiority, open-label study evaluating the efficacy, safety, and tolerability of switching to CAB LA + RPV LA from current INI- NNRTI-, or PI-based antiretroviral regimen in HIV-1-infected adults who are virologically suppressed. ATLAS participants randomized to the SOC, “current antiretroviral” treatment arm, consisting of 2 nucleoside reverse transcriptase inhibitors (NRTIs) plus a third agent (INI, NNRTI, or a PI), or the CAB LA + RPV LA Q4W arm, who successfully complete Week 52 (at minimum) of ATLAS, and remain virologically suppressed (HIV-1 RNA <50 c/mL), will be eligible to enter ATLAS-2M.

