#### **4.2.2.2. Participants transitioning from ATLAS and currently receiving CAB LA + RPV LA Q4W**

Subjects receiving Q4W injections within ATLAS and randomized to receive Q4W injections in Study 207966 will continue receiving maintenance injections Q4W as scheduled and will not require a loading dose on Day 1.

Subjects receiving Q4W injections within ATLAS and randomized to receive Q8W injections in Study 207966 will receive doses of CAB LA 600 mg + RPV LA 900 mg on Day 1, one month after their last Q4W maintenance dose, in order to align with Day 1 of study randomization. Subjects will not require an intermediate dose at Week 4 and will receive their next Q8W maintenance injections at Week 8 and Q8W thereafter.

Participants transitioning from the ATLAS study and on CAB LA + RPV LA Q4W treatment will be randomized at Day 1 to either continue Q4W administration or transition to Q8W administration of CAB LA + RPV LA. The first injection visit for the ATLAS-2M study can be performed once the final central lab results from the ATLAS study are available and safety parameters have been reviewed. Screening labs determining eligibility for ATLAS-2M can be collected at Week 48 (at minimum) for participants originally randomized to the Q4W arm within ATLAS. Screening labs for participants who transitioned from SOC to Q4W injections within the ATLAS Extension Phase may be obtained at ATLAS Week 56b (following the CAB + RPV Oral lead-in period) or at subsequent ATLAS visits after receiving one set or a short course of Q4W injections. The transition from the final ATLAS to ATLAS-2M Day 1 dosing must occur 4 weeks ( $\pm 7$  days) from the final injections received in ATLAS

Dosing for participants transitioning from CAB LA + RPV LA Q4W in ATLAS is as follows:

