##### **4.2.2.2.2. IM injections every 8 weeks (Q8W from ATLAS Q4W):**

Participants transitioning from ATLAS and randomized to receive CAB LA + RPV LA Q8W injections will initiate Q8W dosing at the Day 1 visit as follows:

Day 1- CAB LA 600 mg + RPV LA 900 mg IM, each given as 1 X 3 mL IM injection

Week 8 and Q8W thereafter- CAB LA 600 mg + RPV LA 900 mg IM, each given as 1 X 3 mL IM injection

The second loading injection will be administered at Week 8 (CAB LA 600 mg + RPV LA 900 mg), with subsequent injections (CAB LA 600 mg + RPV LA 900 mg) occurring every 8 weeks thereafter. There will be a -7-day dosing window for the second and third IM injections such that the second injection occurs within the window of Week 7 and Week 8 but no later than Week 8 and third injection occurs within the window of Week 15 and Week 16 but no later than Week 16. Subsequent injections with CAB LA 600 mg and RPV LA 900 mg will occur every 8 weeks ( $\pm 7$  days). Starting after the Week 16 injections, the interval between injection visits will be limited to a maximum of 9 weeks. If the length of time between injections exceeds, or is projected to exceed 9 weeks, the Medical Monitor must be contacted to discuss individual participant case management.

The primary study analysis will consist of data collected through the Week 48 visit. A single repeat of HIV-1 RNA for any participant with a HIV-1 RNA  $\geq 50$  c/mL at Week 48, Week 96, or Week 152 must be performed. The retest should be scheduled as soon as possible (but no later than 4 weeks from the Week 48, 96 or 152 visits, respectively) and will inform the Week 48, 96, or 152 virological endpoint, respectively.

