**Table 7 Dosage and Administration**

Maintenance Phase and Extension Phase (Day 1 to End of Study+)	
Q4W Arm - Transitioning from SOC	
Oral Lead-In	
Day 1 to Week 4b (2 tablets once daily)	
 
• Take 1 tablet CAB 30 mg once daily.
 
• Take 1 tablet RPV 25 mg once daily.
 
 
Should be taken together once daily at approximately the same time each day, with a meal.

First Injections (Loading Dose) – Week 4b	
Week 4b (two 3mL injections once)	
 
• Receive last dose of oral CAB + RPV regimen
 
• Receive CAB LA 600 mg given as 1 X 3 mL IM injection
 
• Receive RPV LA 900 mg given as 1 X 3 mL IM injection
 

Maintenance Injections – every 4 Weeks (Q4W) following Week 4b	
Week 8 to End of Study + (two 2 mL injections every 4 weeks)	
 
• Receive CAB LA 400 mg given as 1 X 2 mL IM injection
 
• Receive RPV LA 600 mg given as 1 X 2 mL IM injection
 

Q8W Arm-Transitioning from SOC	
Oral Lead-In	
Day 1 to Week 4b (2 tablets once daily)	
 
• Take 1 tablet CAB 30 mg once daily.
 
• Take 1 tablet RPV 25 mg once daily.
 
 
Should be taken together once daily at approximately the same time each day, with a meal.

First Injections (Loading Doses) – Week 4b	
Week 4b (two 3 mL injections once)	
 
• Receive last dose of oral CAB + RPV regimen
 
• Receive CAB LA 600 mg given as 1 X 3 mL IM injection
 
• Receive RPV LA 900 mg given as 1 X 3 mL IM injection
 

Maintenance Injections – every 8 Weeks (Q8W) following Week 8	
Week 8 to End of Study+ (two 3mL injections every 8 weeks)	
 
• Receive CAB LA 600 mg given as 1 X 3 mL IM injection
 
• Receive RPV LA 900 mg given as 1 X 3 mL IM injection
 

Q4W Arm – Continuing Q4W injections from ATLAS	
Day 1 to End of Study+ (two 2 mL injections every 4 weeks)	
 
• Receive CAB LA 400 mg given as 1 X 2 mL IM injection
 
• Receive RPV LA 600 mg given as 1 X 2 mL IM injection
 

Q8W Arm- Transitioning from ATLAS Q4W	

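### For participants entering on ATLAS Q4W injections, the Week 8 reference of the PIN change score falls after randomisation and after the two arms' injections have diverged, so it can remove or distort a regimen difference

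*Protocol*

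**What the plan says.** Protocol Section 3 (and the same row in Section 1.2) sets the PIN endpoint as "Change from Week 8 in Dimension scores", together with individual item scores. PIN is collected at Weeks 8, 24, 48 and 152 or at withdrawal, and not at Day 1. The HRQoL, HIVTSQs and ACCEPT change scores under the same objective use Day 1. The footnotes to the Time and Events tables (Section 7.1) place questionnaires at the start of a visit, so the Week 8 PIN comes before the Week 8 injections.

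Section 4.2.2.2 says that participants arriving on ATLAS Q4W injections "will be randomized at Day 1 to either continue Q4W administration or transition to Q8W administration of CAB LA + RPV LA". Those assigned to Q8W receive, under Section 4.2.2.2.2, "Day 1- CAB LA 600 mg + RPV LA 900 mg IM, each given as 1 X 3 mL IM injection", and Section 4.2.2.2 adds: "Subjects will not require an intermediate dose at Week 4". Those assigned to Q4W receive 2 mL of each drug at Day 1 and every four weeks after that (Section 4.2.2.2.1; Table 7 in Section 6.3). Participants arriving on oral SOC have an oral lead-in, and in both arms a 3 mL injection of each drug at Week 4b (Sections 4.2.2.1.1 and 4.2.2.1.2).

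One Week 8 reference therefore serves both entry groups.

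**The concern.** A change score gives a clean between-arm comparison when its reference value cannot have been affected by the assigned treatment. For ATLAS Q4W entrants the Week 8 PIN is measured eight weeks after randomisation, when the two arms have already had different injection schedules. It is an early outcome used as a baseline. Subtracting it also subtracts whatever difference the regimens have produced by then.

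Section 2.2 says the study will assess injection tolerability of both regimens, and PIN is its injection-specific instrument. Section 4.4 defends the open-label design partly because it keeps patients with Q4W experience, so that the two regimens can be compared within a person. For a patient moved from Q4W to Q8W, change from Week 8 compares later Q8W experience with early Q8W experience. It does not describe the switch.

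**Working it through.** The protocol text at hand states no power, alpha or test for PIN, so there is no figure to reproduce. The check has two steps.

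**Step 1. Nominal injections received before the Week 8 PIN** (Sections 4.2.2.1.1 to 4.2.2.2.2; Table 7)

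| Entry group, arm | Injection visits | Volume per drug, each visit | Total per drug | Weeks since last injection |
|---|---|---|---|---|
| Oral SOC, Q4W | Week 4b | 3 mL | 3 mL | 4 |
| Oral SOC, Q8W | Week 4b | 3 mL | 3 mL | 4 |
| ATLAS Q4W, Q4W | Day 1, Week 4 | 2 mL | 4 mL | 4 |
| ATLAS Q4W, Q8W | Day 1 | 3 mL | 3 mL | 8 |

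Oral SOC entrants have the same exposure in both arms. ATLAS Q4W entrants differ by arm in number, volume and interval.

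**Step 2. What the change score estimates.** Let D be the between-arm difference in score at a later visit, taken as equal in both entry groups. Let E be the between-arm difference at Week 8 among ATLAS Q4W entrants, and f their share of participants. The Week 8 difference among oral SOC entrants is taken as 0, because their injections have been the same. Then

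pooled difference in change = (1 − f) × D + f × (D − E) = D − f × E.

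With g = E/D, this is D × (1 − f × g), so the share removed is f × g. Neither f nor g is in the documents. The values below are assumptions that show the range.

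| Share of D retained | g = 0 | g = 0.5 | g = 1 |
|---|---|---|---|
| f = 0.25 | 100% | 87.5% | 75% |
| f = 0.5 | 100% | 75% | 50% |
| f = 0.75 | 100% | 62.5% | 25% |
| f = 1 (within the ATLAS Q4W group) | 100% | 50% | 0% |

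A simulation with a later difference of 0.30 SD agrees with the formula. At f = g = 0.5 it gave 0.226 (formula: 0.30 × 0.75 = 0.225). At f = 0.5, g = 1 it gave 0.154 (0.30 × 0.5 = 0.15). At f = g = 1 it gave −0.008 (formula: 0).

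**Direction.** The loss lies between none and all only if g is between 0 and 1. Within the ATLAS Q4W group, g = 1.5 gives 1 − 1.5 = −0.5, a reversed sign, and g = −0.5 gives 1 + 0.5 = 1.5, an inflated difference. If the later difference is zero but an early one existed, the pooled contrast is −f × E, a difference that is not there at the later visit.

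**The case against.** The strongest reply is that nothing in the protocol text at hand makes PIN change a formal between-arm contrast. The objective in that row says assess, whereas the efficacy, safety and preference objectives are worded as comparisons. As a description of how people adapt to injections over time, change from the first PIN visit is coherent. Week 8 also has a good reason behind it: oral SOC entrants have no study injection to rate at Day 1, and Week 8 is the first scheduled visit by which everyone has had one. Sections 7.8 and 9.3.7 and any SAP were not available for this check and may already compare scores by visit or by stratum. No data are lost either, since the scores themselves are collected.

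Most of this stands, and it limits the weight of the point. It does not repair the definition. Section 3 fixes one post-randomisation reference for both entry groups in a randomised comparison of two regimens, and a reader would naturally set the two arms' changes side by side.

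A reader might also infer that most of the trial is affected, because Section 1.1 says "The majority of participants in ATLAS-2M will rollover from the ongoing 201585 (ATLAS) trial". The documents do not support that. The same section says that rollovers include participants on oral SOC, for whom Week 8 works, and the share entering on Q4W injections is not given.

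**Conclusion.** The point holds for ATLAS Q4W entrants, and for any pooled between-arm comparison of PIN change that includes them. For oral SOC entrants Week 8 is a fair reference.

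The share of the later difference removed overall is f × g, and neither quantity is in the documents. Within the affected group the loss runs from none, if the regimens do not differ on PIN by Week 8, to all, if the difference is already complete by then. Two stronger statements might be inferred and are not supported: that a known share of the effect disappears, and that the bias is always toward no difference. The first needs values for f and g. The second needs the Week 8 and later differences to have the same sign, with the earlier one no larger.

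This concerns a secondary patient-reported endpoint with no test or power stated in the text at hand. The primary virological conclusion is unaffected. The change is still worth making because it costs almost nothing.

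**What to change.** For any between-arm PIN comparison, compare the scores at Weeks 24, 48 and 152, stratified by prior CAB + RPV exposure (0, 1–24 and >24 weeks). These are the randomisation strata in Section 4.1, so the comparison within each stratum is a randomised one. Use Week 8 as a baseline or covariate only in the 0-week stratum. In ATLAS Q4W entrants, keep change from Week 8 as a within-arm description of experience on the assigned regimen, and label it so. If Section 9.3.7 or the SAP already does this, only the endpoint wording in Sections 1.2 and 3 needs aligning.

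The cost is wording. All the scores are already scheduled, so no new data are needed. The downside is slightly lower precision in the prior-exposure strata, where there is no baseline adjustment.
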